#### **4.4 Inclusion and Exclusion Criteria**

The inclusion criteria are as follows:

1. Woman  $\geq$ 18 years and  $<$  80 years of age;
2. Classified as BI-RADS 4C or 5;
3. Lesion depth is  $\leq$  6 cm from skin surface;
4. Non-palpable lesions;
5. Informed consent obtained.

The exclusion criteria are as follows:

1. Multicentric breast cancer;
2. Pregnant or lactating;
3. Known or suspected nickel-titanium allergy.

#### **4.5 Design**

This is a single-arm, multicenter, non-randomized cohort study that will include five hundred (500) participants scheduled to undergo a biopsy of a breast lesion at participating Canadian and US study centers.

The expected duration of the trial is 12-18 months. Enrollment is expected to take approximately 12 months.

The primary endpoint of this cohort will be compared to historical controls (standard of care visits).

The registry is divided into three periods:

1. Inclusion Period: from registry eligibility screening until reflector insertion;
2. Device Period: from reflector insertion at biopsy to removal at surgery;
3. Outcomes Period: from completion of surgery to pathology report of outcomes.

#### **4.6 Inclusion Period**

Patients meeting all inclusion criteria and no exclusion criteria will be considered for inclusion into the registry. Each eligible patient will be informed about the registry by the Investigator or designate.

Prior to any data collection, the patient must be thoroughly informed about all aspects of the registry and must have signed the Research Ethics Board (REB) or Institutional Review Board (IRB) approved Informed Consent Form (ICF). Participants will be assigned a unique identifier for the registry upon enrollment.

No patient data, including adverse events will be collected in this period. A patient will be considered enrolled in the registry at the time of reflector insertion.

#### 4.6.1 Informed Consent Process

Written Informed Consent with the REB/IRB approved consent form will be obtained for all subjects prior to conducting any study-related assessments and prior to administration of any pre-procedure medications or sedation. The principal investigator, or qualified designee, will explain to each patient all aspects of the clinical study that are relevant to the patient's decision to participate in the clinical study including, but not limited to, the following: purpose and nature of the study, study procedures, expected study duration, available alternative therapies, the benefits and risks involved with study participation and the potential treatment. The principal investigator, or qualified designee, shall avoid any coercion or undue improper influence on, or inducement of, the patient to participate and will not waive or appear to waive the patient's legal rights. Patients will be given a copy of the informed consent form and will be provided ample time to read and understand the document and be given the opportunity to ask questions. Patients will be informed of their right to withdraw from the study at any time without prejudice; consent forms will use non-technical language and be provided in a language understandable to the patient. After this explanation, and before any study-specific procedures have been performed, the patient and the principal investigator, or qualified designee, responsible for conducting the informed consent process will voluntarily sign and personally date the ICF. The patient will receive a copy of the signed and dated written informed consent.

The informed consent process may be completed during an in-person meeting or through remote consent procedures. All procedures of remote consent must be in compliance with institutional requirements for remote consent.

The principal investigator or qualified designee will document in the medical records on the informed consent document the informed consent process, including the date of consent and name of the person conducting the consent process. Documentation of the time of consent is required if the informed consent process occurs on the same day as the index procedure. The principal investigator or qualified designee shall ensure important new information is provided to new and existing participants throughout the clinical investigation.

#### 4.7 Device Period

Insertion of the SCOUT® Reflector shall be conducted according to the IFU at the time of biopsy. The physician will follow regular clinical practice before and during the biopsy procedure.

SCOUT® Reflector may be inserted in a soft tissue biopsy site or a soft tissue site intended for surgical removal as per IFU and clinician decision. Additionally, as per clinician decision, more than one (1) SCOUT® Reflector may be inserted in a participant (bracketing) ensuring a minimum distance of 25 mm between Reflectors.

The data collected during the biopsy and reflector insertion will consist of the following:

- Patient demographic: age, weight, height and diagnosis
- Date of assessment
- Date of biopsy and insertion
- Reflector insertion data: success, deployment within lesion or distance from lesion, depth of reflector, type of guidance used, number of reflectors used, type of lesion
- Lot number(s) and model of the SCOUT® Reflector

- Reflector detection (if performed)
- Adverse events (if applicable)

The data collected during the surgery will consist of the following:

- Date of surgery
- Neoadjuvant therapy (if applicable): start and stop date
- Reflector detection: success before or after incision
- Reflector retrieval data: success, identification and retrieval duration
- Operative time: Time from beginning the detection to the time the lesion is removed from the breast.
- Participant satisfaction questionnaire: this may be completed by/collected from the participant up to 2 weeks after the surgery.
- Adverse events (if applicable)

#### **4.8 Final Outcomes**

The assessment of procedure success is determined by the pathology report. This will not require an additional participant visit for the purposes of the registry. Participation will be considered complete following collection of the final outcomes and Participant satisfaction questionnaire.

The following data points will be recorded from the report:

- Excised tissue information
- Specimen size
- Margins: (positive, close, negative)
- Re-excision required (after surgery)
- Radiologist assessment (collected once per radiologist at completion of study)
- Surgeon assessment (collected once per surgeon at completion of study)

---

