Inclusion / Exclusion Criteria:	
Inclusion Criteria:
 
 
1. Woman <math>\geq 18</math> years and <math><80</math> years of age;
 
2. Classified as BI-RADS 4C or 5;
 
3. Lesion depth is <math>\leq 6</math> cm from skin surface;
 
4. Non-palpable lesions;
 
5. Informed consent obtained.
 
 
Exclusion Criteria:
 
 
1. Multicentric breast cancer;
 
2. Pregnant or lactating patient;
 
3. Known or suspected nickel-titanium allergy.
 

Study Product / Intervention:	SCOUT® Reflector, SCOUT® Console, SCOUT® Handpiece -all components of the SCOUT® Surgical Guidance System.
Control Intervention (if applicable):	The primary endpoint of this cohort will be compared to historical standard of care.
Number of Participants:	Five hundred (500) BI-RADS 4C/5 patients undergoing biopsy of a breast lesion at a participating study center.
Study Duration:	12 -18 months
Study Schedule:	
Reflector Insertion: Device (Reflector) will be inserted in eligible, consented participants at the time of biopsy as per the instructions for use.
 
Surgery: Reflector will be detected and retrieved at the time of breast surgery. Reflector performance and safety will be assessed based on detection and retrieval success and the rate of adverse events.
 
Pathology report: Results from the pathology report will be recorded. Procedural success defined as the absence of close margins (DCIS: <2mm), positive margins (tumor on ink) or requirement for re-excision.
 
No post-operative participant follow-up will be required.

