## 2. Background and Rationale

### 2.1 Breast Cancer: Clinical Background

Breast cancer continues to be a consequential disease posing a considerable burden on patients, families and the healthcare system. One in eight women are expected to develop breast cancer in their lifetime. In Canada, it is estimated that 28,600 women will be diagnosed with breast cancer in 2022. In the United States (US), 281,550 new cases of breast cancer were estimated in 2021.

Due to increased utilization of mammographic screening and improved imaging techniques, there has been a rapid increase in the detection of palpable and non-palpable breast lesions. This increased detection rate of non-palpable breast lesions has increased the need for imaging-guided localization before surgery. Localization plays an important role in conservative surgical excision, with or without neoadjuvant therapy. The goal of breast conserving surgery (BCS) is to safely remove the target tissue with adequate surgical margins (SM), avoid unnecessary resection of healthy breast tissue, providing a good cosmetic outcome without compromising survival. Re-excision rates in Canada have been previously reported as high as 23% and in the US 22.6%.

Currently lesions are classified based on the Breast Imaging, Reporting and Data System (BI-RADS, American College of Radiology). Lesion categorization provides an estimated risk of malignancy based on imaging findings. BI-RADS classification of 4C or 5 estimate risk of malignancy to be >50% and >95% respectively. These patients are considered highly likely to receive surgical intervention.

**Table 2.** Risk of Breast Cancer.a

Indication	Risk of malignancy
BI-RADS 5	>95%
BI-RADS 4C	>50%-95%
BI-RADS 4B	>10%-50%
BI-RADS 4A	>2%-10%
New breast problem for diagnostic workup	2.5%-6.5%
BI-RADS 3	≤2%
High-risk screening	~1%
Intermediate risk screening	0.8%
Average risk screening	0.5%

Abbreviation: BI-RADS, Breast Imaging, Reporting & Data System.

aBreast biopsy of lesion: 30% to 40% overall risk of malignancy subdivided according to BI-RADS assessment.

FIGURE 1: RISK OF BREAST CANCER: BI-RADS

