### **4.2 Endpoints**

The primary endpoint is the number of patient visits to the breast center for invasive procedures from the time of biopsy to surgery. The primary endpoint will be compared to historical controls. It is expected that there will be a mean reduction of at least one (1) visit for invasive procedures.

The secondary endpoints are defined below:

1. Device success: percent successful localization, detection and retrieval.
2. Device safety: rate of device-related adverse events.
3. Procedural success: absence of close margins (<2mm), positive margins (tumor on ink) or requirement for re-excision.
4. Duration (days) from diagnosis to surgery and biopsy to surgery.
5. Radiologist assessment: ease of placement; ability to position reflector in desired location; scheduling flexibility; visibility on ultrasound/ mammography (immediate and late); artifact (Tomo/MRI if applicable).
6. Surgeon assessment: ease of detection; ease of device retrieval.
7. Participant satisfaction questionnaire: anxiety; convenience; pain; overall experience compared to expectation
8. Process improvement with implementation of same-day biopsy and SCOUT® Reflector placement.

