### Schedule of Assessments

	Consent*	Biopsy**	Surgery	Final Outcomes***
Patient Data				
Informed Consent	X			
Demographic information (age, height, weight, diagnosis)		X		
Neoadjuvant therapy (start and stop date)			X	
Device and Procedural Data				
Reflector insertion data (success, deployment within lesion or distance from lesion, depth of reflector, type of guidance used, number of reflectors used, type of lesion, reflector detection)		X		
Reflector detection (before incision or after incision)		X i	X	
Reflector retrieval (success, identification and retrieval duration)			X	
Operative time			X	
Adverse events (including device deficiencies)		X	X	
Scheduling Data				
Date of assessment		X		
Date of biopsy and insertion		X		
Date of surgery			X	
Satisfaction Assessments				
Radiologist assessment: ease of placement; ability to position reflector in desired location; scheduling flexibility; visibility on ultrasound/mammography; artifact (Tomo/MRI if applicable)				X ii
Surgeon assessment: ease of detection; ease of reflector removal				X ii
Participant satisfaction questionnaire			X iii	

Pathology Report data				
Margins (positive; close <2mm; negative >2mm)				X
Re-excision required (after surgery)				X
Excised tissue information				X

\*Performed prior to biopsy

\*\*Reflector insertion performed at time of biopsy

\*\*\*No additional participant visit; data recorded from pathology report

i If performed

ii Collected once per clinician at completion of registry

iii Window up to 2 weeks post-surgery (remote completion)

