4.4 Study Assessments

	Consent*	Biopsy**	Surgery	Final Outcomes***
Patient Data				
Informed Consent	X			
Demographic information (age, height, weight, diagnosis)		X		
Neoadjuvant therapy (start and stop date)			X	
Device and Procedural Data				
Reflector insertion data (success, deployment within lesion or distance from lesion, depth of reflector, type of guidance used, number of reflectors used, type of lesion, reflector detection)		X		
Reflector detection (before incision or after incision)		X ⁱ	X	
Reflector retrieval (success, identification and retrieval duration)			X	
Operative time			X	
Adverse events (including device deficiencies)		X	X	

Scheduling Data				
Date of assessment		X		
Date of biopsy and insertion		X		
Date of surgery			X	
Satisfaction Assessments				
Radiologist assessment: ease of placement; ability to position reflector in desired location; scheduling flexibility; visibility on ultrasound/mammography; artifact (Tomo/MRI if applicable)				X ⁱⁱ
Surgeon assessment: ease of detection; ease of reflector removal				X ⁱⁱ
Participant satisfaction questionnaire			X ⁱⁱⁱ	
Pathology Report data				
Margins (positive; close <2mm; negative >2mm)				X
Re-excision required (after surgery)				X
Excised tissue volume/weight & specimen size				X

^{*}Performed prior to biopsy

^{**}Reflector insertion performed at time of biopsy

^{***}No additional participant visit; data recorded from pathology report

ⁱIf performed

ⁱⁱCollected once per clinician at completion of registry

ⁱⁱⁱWindow up to 2 weeks post-surgery (remote completion)

Identification of any number ranges for numeric endpoints along with their corresponding text descriptors.

- Continuous variables will be collected for: age, weight, height, operative time and adverse event rate, duration between events
- Categorical variables will be established for device success, procedural success, clinician assessment, participant satisfaction

5 Sample Size

No formal sample size calculation has been performed. Five hundred (500) participants will be included in this registry. This sample size has been selected to adequately support a multi-center experience reflective of the Canadian healthcare system and associated workflow.

Further, the Canadian Agency for Drugs and Technologies in Health (CADTH) assessed the evidence of STREAMLoc_Statistical Analysis Plan v1.0_30AUG2021

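### Re-excision is recorded from the pathology report and the Outcomes Period ends there, although the decision follows the report; procedural success may be overstated by an amount the documents do not fix

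*Protocol*

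**What the plan says.** Protocol 4.2 defines procedural success as "absence of close margins (<2mm), positive margins (tumor on ink) or requirement for re-excision". The protocol synopsis and SAP 3.2 use the same three components but limit the close-margin criterion to DCIS.

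On the source, Protocol 4.8 states: "The assessment of procedure success is determined by the pathology report". It then introduces its list with "The following data points will be recorded from the report", and a need for re-excision is on that list. The Protocol Schedule of Assessments puts the item in its pathology block, and the footnote to that column reads "No additional participant visit; data recorded from pathology report". SAP 4.4 has the same row, "Re-excision required (after surgery", in the same block with the same footnote.

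On timing, Protocol 4.5 gives "Outcomes Period: from completion of surgery to pathology report of outcomes"; the synopsis and SAP 4.1 agree. The synopsis adds "No post-operative participant follow-up will be required". The only participant-level item allowed later is the satisfaction questionnaire, up to 2 weeks after surgery, and its listed content does not cover re-excision.

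Neither document names another source for re-excision or a time window for it. SAP 7.1 maps procedural success to the margin assessment field of the Outcomes CRF and to nothing else.

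**The concern.** A pathology report describes the specimen. Whether a further operation is needed is decided by surgeon and patient after they have read it. The plan therefore takes a later decision from a document that precedes it, and closes the period at that document.

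A site that follows this text has two natural courses. It can infer re-excision from margin status, in which case the third component repeats the first two and may record a need that never arises. Or it can enter no because nothing has been decided, in which case a later decision is lost and the participant may be scored a success.

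The third component does its own work only where the margin is not already scored as a failure. Under the synopsis and SAP wording, a close but not positive margin in a non-DCIS lesion is such a case: it can fail only through re-excision. These are judgement cases settled after the report, so the stated source is weakest where the component matters most.

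Re-excision is also an outcome that the protocol's background puts a number on: "Re-excision rates in Canada have been previously reported as high as 23" per cent, and 22.6% in the US. Readers may set the registry's figure beside these.

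**Working it through.** The plan gives no expected re-excision or procedural success rate, so there is no figure to reproduce. The check is a comparison of the texts, then a sensitivity calculation.

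**Texts side by side**

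| Question | Where | Answer |
|---|---|---|
| Is re-excision part of the endpoint? | Synopsis; Protocol 4.2; SAP 3.2 | Yes |
| What is its source? | Protocol 4.8; both schedules | Pathology report |
| When does collection end? | Synopsis; Protocol 4.5; SAP 4.1 | At that report |
| Is there another source or a later look? | Neither document | None stated |
| Which field feeds the endpoint? | SAP 7.1 | Margin assessment only |

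**Inputs**

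- Operated participants: 500 planned (Protocol 5.1), at most 10% without surgery (Protocol 5.2), so 500 × 0.90 = 450. Endpoints use the per-protocol set (Protocol 5.3).
- Background re-excision rate: 23% (Protocol 2.1).
- *f*, the share of re-excisions not captured: not in the documents; assumed.
- *m*, the share with a margin already scored as failure: assumed 15% to 25%.
- *q*, the re-excision rate among the rest: assumed 1% to 5%.

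**Re-excision component.** Recorded rate = true rate × (1 − *f*). At 23%, the expected number is 450 × 0.23 = 103.5.

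| *f* (assumed) | Recorded rate | Missed |
|---|---|---|
| 10% | 23% × 0.90 = 20.7% | 10.4 |
| 25% | 23% × 0.75 = 17.25% | 25.9 |
| 50% | 23% × 0.50 = 11.5% | 51.8 |

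**Composite.** True failure is *m* + (1 − *m*)*q*. With under-capture it is recorded as *m* + (1 − *m*)*q*(1 − *f*). The understatement is (1 − *m*)*q f*.

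| *m* | *q* | *f* | Understatement | Of 450 |
|---|---|---|---|---|
| 25% | 1% | 25% | 0.75 × 0.01 × 0.25 = 0.19 points | 0.8 |
| 20% | 3% | 50% | 0.80 × 0.03 × 0.50 = 1.20 points | 5.4 |
| 15% | 5% | 100% | 0.85 × 0.05 × 1.00 = 4.25 points | 19.1 |

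**SAP 7.1 read literally.** If only the margin field enters, no re-excision without a margin failure counts, whatever the site records. That is *f* = 100% for the composite: from 0.75 × 0.01 = 0.75 points (3.4 of 450) to 4.25 points (19.1 of 450).

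**Over-recording.** Let *r* be the share of participants without a scored margin failure who are wrongly recorded as needing re-excision. The net understatement is (1 − *m*)(*q f* − *r*), which changes sign if *r* exceeds *q f*. Over-recording among participants whose margins already fail raises the component but leaves the composite unchanged.

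**The case against.** The strongest reply is that Protocol 4.8 is loosely worded and does not restrict the source. The same list holds the radiologist and surgeon assessments, collected once per clinician at study end, which cannot come from a pathology report. Protocol 6.3 accepts medical records as source documents and wants the eCRF kept current. Protocol 6.5 allows for remote access to electronic records for verification. Protocol 5.2 ties completion to documentation of surgical outcomes. The statements on follow-up and visits concern the participant and do not bar a chart entry. All of this stands. A reader might infer that later re-excisions are bound to be missed; the documents do not support that, because a site could use the chart. But nothing tells it to, the schedule footnotes point elsewhere, and sites may differ in source and date.

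Second, the item is a requirement for re-excision, not a completed operation, so it arises nearer to the report. This reduces the likely loss but does not remove it.

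Third, the direction is not strictly fixed. Inference from margins can over-record, and a model of under-capture alone has its direction built in. This also stands: loss of later decisions is the main risk, not the only one.

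Fourth, a reader might infer a biased comparison with 23% or 22.6%, or take the fall in the component as the effect on the endpoint. The documents support neither. The registry tests no hypothesis, only the primary endpoint is to be compared with historical data, and a separate re-excision rate is not a listed endpoint.

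**Conclusion.** The point holds as a defect of source and timing. The written rule takes re-excision from a document that precedes the decision and closes the Outcomes Period there. Followed as written, it makes the component redundant or incomplete, and the main risk is that procedural success reads too high.

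The size cannot be found from the documents. The composite range of about 0.2 to 4.3 percentage points rests entirely on assumed values of *m*, *q* and *f* and allows for no over-recording; its top needs every re-excision without a margin failure to be lost. Which close-margin wording applies also matters: if close margins of any histology count, as in Protocol 4.2, fewer cases depend on the re-excision component than under the synopsis and SAP wording. The two wordings need to be reconciled.

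This is a descriptive secondary endpoint, so no primary conclusion is at risk. The change is still worth making, because the remedy is cheap.

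**What to change.** - In Protocol 4.8 and both schedules, move re-excision out of the pathology block. Record yes/no, date and reason from the surgical or medical record, by one remote chart check at a fixed time after surgery chosen by the sponsor. No participant visit is needed.
- Extend the Outcomes Period to that check for this item only, in the synopsis, Protocol 4.5 and SAP 4.1. Margins stay with the pathology report.
- Amend SAP 7.1 so that procedural success uses the re-excision field as well as the margin field. Without this, a re-excision found in the chart might still not enter the endpoint.

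The cost is protocol, SAP and CRF wording, one chart check per operated participant (about 450 if 10% have no surgery), somewhat later data closure for the last participants, and possibly a less favourable success rate. Medical records already serve as eCRF source, so no new kind of source is needed.
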